8.4.1 Primary Efficacy Analysis

The aim of this study is to demonstrate that in terms of the primary efficacy endpoint, 50% relative reduction in SALT score at Week 24, CTP-543 is superior to the placebo. Pairwise treatment group differences will be assessed with the χ^2 test.

The active treatment will be considered effective if $p \leq 0.05$.

Number and percentage, as well as p-values based on the χ^2 test, will be reported for the responders, defined as a patient meeting at least 50% relative reduction in SALT score at Week 24. Additionally, the number and percentage of responders will be reported by alopecia areata subtype.

Responders will be presented graphically by treatment group as a bar graph at 24 Weeks and as a line graph across time.

8.4.2 Exploratory Efficacy Analyses

Treatment differences for absolute score, absolute change, and relative change in SALT score from baseline to Weeks 4, 8, 12, 16, 20, and 24 will be assessed with a mixed-effect model of repeated measures (MMRM). The model will include fixed factors for treatment group, study visit, treatment by study visit interaction, and alopecia areata subtype, with baseline SALT score as a covariate. An unstructured variance-covariance matrix will be used. If convergence is not achieved, an alternative autoregressive covariance structure will be used. If the MMRM model does not converge, other covariance structures will be explored. If convergence is still not met, only descriptive statistics will be presented.

Point estimates and standard errors will be presented for each treatment group at each time point. P-values for the treatment by visit interaction will be presented at Week 24 for each active treatment compared to the placebo. A comparison of the active doses (4 mg vs. 8 mg, 4 mg vs. 12 mg, 8 mg v. 12 mg) will be presented as well. Treatments will be compared overall and by visit.

Descriptive statistics will be reported for the SALT score at each time point for each treatment group and by subtype. By-patient data listing will also be presented for patient SALT scores and collection of SALT photographs. The mean of observed value, absolute change, and relative change SALT scores along with standard errors for each treatment group will be presented using line graphs.

Responders, as defined for the primary endpoint, will be analyzed per section 8.4.1 for Weeks 4, 8, 12, 16, and 20. Additionally, the following responder groups will be analyzed per section 8.4.1 at Weeks 4, 8, 12, 16, 20, and 24: 1) patients who meet at least 75%, 90%, and 100% relative change; 2) patients who meet an absolute SALT score of ≤ 10 , ≤ 20 , or ≤ 25 .

The percent change in clinician and patient VAS-S from baseline will be assessed using the analysis of covariance (ANCOVA) for Week 12 and 24 with fixed factors for treatment, alopecia areata subtype, and baseline VAS-S. The least squares mean score estimates with 95% CI will be presented along with p-values for each treatment comparison at each time point. Descriptive statistics will also be reported by treatment and subtype.

A χ^2 trend test will be used to analyze CGI-I and PGI-I between treatment groups overall. Responses for PGI-I and CGI-I categorized as achieving “Very Much/Much Improved” or “Much/Very Much Worse” will also be compared between treatment groups with the χ^2 test. Descriptive statistics and by-patient data listings will also be presented for the 7 response categories for each assessment.

Mean and mean change from baseline for total AASIS score will be reported. Number and percentage of subjects in each response category of AASIS will also be summarized. Individual responses will be listed in categories of “Severity” and “Interference”.

The exploratory questions will be summarized with descriptive statistics at baseline and Week 24, and will be listed in the by-patient data listings. Responses will be categorized as “Satisfied” (including responses of “Very satisfied” and “Satisfied”) and “Unsatisfied” (including responses of “Unsatisfied” and “Very unsatisfied”) and presented as a 2 x 2 shift table from baseline to Week 24, compared with a χ^2 Test by cohort.

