2.6 Sample Size Determination

There are very few studies in the literature to provide reliable estimates of active treatment or placebo response rates using SALT, or the estimate of variances around these measures, in patients with alopecia areata. Power calculations assume a 2-sided chi-squared test and significance level of 0.05 and are based on an active treatment response rate of 45% and a placebo response rate of 10%.

Although patients will be randomized in an unbalanced ratio of active drug to placebo within each cohort, the placebo patients from the 3 cohorts will be combined for statistical comparisons to each active treatment group. The first 2 cohorts will be randomized in a 2:1 ratio (active:placebo) and the third cohort will be randomized in a 5:1 ratio (active:placebo). Based on estimated completion rates, this randomization scheme is expected to provide a similar number of patients in each CTP-543 dose group and the pooled placebo group. Thus, power calculations for the comparison to placebo are based on a 1:1 treatment ratio of each CTP-543 dose group to placebo. Power calculations assume a 2-sided test and significance level of 0.05 and are based on an active treatment response rate of 45% and a placebo response rate of 10%. Based on estimated completion rates as of Amendment 4, this randomization scheme is expected to provide a similar number of patients in the 12 mg group and the pooled placebo group.

A sample size of 28 patients in the 12 mg group and 28 patients in the pooled placebo group will provide >80% power for the chi-squared test when comparing each dose group to the combined placebo group (28 active, 28 placebo). Approximately 150 patients will be randomized in order to provide 120 patients who complete treatment.

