8.4 Analysis Methods

All statistical tests will be 2-sided with a significance value of 0.05. Testing will be based on the Efficacy population and performed only for the Treatment Period. An analysis of the primary efficacy endpoint and exploratory SALT endpoints will also be performed for the Per Protocol population. The final efficacy analysis will be conducted when all patients in the 12 mg cohort have completed Week 24. The placebo groups from all 3 cohorts will be pooled and compared to each active dose (4 mg, 8 mg, and 12 mg) individually. Active doses, 4 mg, 8 mg, and 12 mg, will also be compared. There will be no adjustment for multiple treatment group comparisons in this dose-ranging Phase 2 study.

Table 8-1 gives an overview of the analysis methods that will be used for each of the efficacy variables.

Table 8-1 Efficacy Variables and Analysis Methods

Efficacy Variables	Collection Times	Method
Primary		
Responder Analysis SALT (50% relative reduction)	Baseline, Week 24	χ^2 Test
Exploratory		
Responder Analysis SALT (50% relative reduction)	Baseline, Week 4, 8, 12, 16, 20	χ^2 Test
Responder Analysis SALT (75%, 90%, and 100% relative reduction)	Baseline, Week 4, 8, 12, 16, 20, 24	χ^2 Test
SALT (≤ 10 , ≤ 20 , ≤ 25 absolute score)	Baseline, Week 4, 8, 12, 16, 20, 24	χ^2 Test
SALT (absolute change)	Baseline, Week 4, 8, 12, 16, 20, 24	MMRM
SALT (relative change)	Baseline, Week 4, 8, 12, 16, 20, 24	MMRM
SALT (absolute score)	Baseline, Week 4, 8, 12, 16, 20, 24	MMRM
Clinician VAS-S (percent change)	Baseline, Week 12, 24	ANCOVA
Patient VAS-S (percent change)	Baseline, Week 12, 24	ANCOVA
CGI-I	Week 12, 24	χ^2 Test
CGI-I Responder (“Very Much/Much Improved” and “Much/Very Much Worse”)	Week 12, 24	χ^2 Test
PGI-I	Week 12, 24	χ^2 Test
PGI-I Responder (“Very Much/Much Improved” and “Much/Very Much Worse”)	Week 12, 24	χ^2 Test
AASIS	Baseline, Week 24	Descriptive Statistics
Exploratory Questions	Baseline, Week 24	Descriptive Statistics
Responder Analysis, Exploratory Questions, Satisfied v. Unsatisfied	Baseline, Week 24	χ^2 Test

χ^2 = Chi-Squared Test; ANCOVA = analysis of covariance; CMH = Cochran-Mantel-Haenszel; MMRM = mixed-effect model for repeated measures

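### The MMRM fallback in SAP 8.4.2 does not require a separate variance at each visit; if it were used, Week 24 p-values for the exploratory SALT endpoints could be too small (minor)

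*SAP*

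**What the plan says.** SAP 8.4.2 fits the MMRM with fixed effects for treatment, visit, their interaction and alopecia subtype, and with baseline SALT as a covariate. The covariance matrix is unstructured. Three steps follow if that fit fails:

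1. "If convergence is not achieved, an alternative autoregressive covariance structure will be used".
2. "If the MMRM model does not converge, other covariance structures will be explored".
3. If nothing converges, only descriptive statistics are shown.

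The SAP does not say whether the autoregressive structure has one variance or one per visit. It gives no order for the structures in step 2, no robust standard error and no degrees-of-freedom method. Protocol 12.4.2 specifies the unstructured matrix with no fallback.

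Week 24 p-values are planned for each dose against placebo and between doses, and treatments are also compared by visit. SAP 8.4 sets the level for all of these: "All statistical tests will be 2-sided with a significance value of 0.05". There is no multiplicity adjustment. The MMRM endpoints are exploratory; the primary Week 24 responder endpoint uses a chi-squared test (SAP 8.4.1).

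**The concern.** Homogeneous AR(1) estimates a single residual variance for all six visits. Change from baseline starts at zero for everyone, so its spread is likely to be small at Week 4 and larger at Week 24, when patients who have regrown hair and patients who have not are far apart. A pooled variance then lies above the true value early and below it late. The Week 24 standard error is too small, and the p-value at the visit of most interest is too optimistic.

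Absolute SALT score is not exempt. With baseline SALT in the model, absolute score and absolute change differ only by a shift in the baseline coefficient, so their residuals are the same.

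The second step adds a smaller problem. If several unnamed structures converge, nothing in the SAP says which one is reported.

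**Working it through.** **The plan's own figure.** The only power figure concerns the primary test. For 28 per group (12 mg against pooled placebo), SAP 2.6 states that this "will provide >80% power for the chi-squared test", at response rates of 45% and 10%. With n = 28 per arm and pooled rate 0.275:

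z = [0.35·√28 − 1.96·√(2·0.275·0.725)] / √(0.45·0.55 + 0.10·0.90) = 1.06, so power is 85.5%.

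The stated figure reproduces. None is given for the MMRM or its fallback.

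**Inputs from the documents**
- Six post-baseline SALT visits, so an unstructured matrix has 6·7/2 = 21 parameters.
- Two-sided level 0.05.
- About 150 randomized and 120 completing (SAP 2.6). With 2:1, 2:1 and 5:1 allocation and equal active groups of size a, pooled placebo is a/2 + a/2 + a/5 = 1.2a and the total is 4.2a. That gives about 29 per dose and 34 placebo among 120, or 36 and 43 among 150.

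**Assumed inputs.** SAP 2.6 says reliable variance estimates are lacking, and no SD by visit is given. I assume a Week 24 SD of 30 points, linear growth from a lower Week 4 SD, and within-patient correlation of 0.7 to 0.95. Only the ratio of SDs matters for the false-positive rate.

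**Limiting calculation.** For a true covariance S, the homogeneous AR(1) fit tends to the matrix A that minimises log|A| + tr(A⁻¹S). If its SD is s, then

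false-positive rate at Week 24 = 2·[1 − Φ(1.96·s/30)].

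Example, 2-fold growth (15 to 30), correlation 0.85: s = 23.37, ratio 0.779, rate 12.7%. The root mean square of the six SDs gives a rough hand check: √[(225 + 324 + 441 + 576 + 729 + 900)/6] = 23.1.

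| SD growth, Week 4 to 24 | SE ratio at Week 24 | Limiting false-positive rate |
|---|---|---|
| none | 1.00 | 5.0% |
| 1.5-fold | 0.84–0.85 | 9.7–9.8% |
| 2-fold | 0.77–0.78 | 12.4–12.9% |
| 3-fold | 0.71–0.73 | 15.0–16.1% |
| 4-fold | 0.69–0.71 | 16.2–17.7% |

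At correlation 0.85, the 4-fold figure is 17.0%. A rate of 15% needs an SE ratio of about 0.73, so roughly 3-fold growth. At Week 4 the error reverses: in the 2-fold case the rate is about 0.2%.

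**Simulation.** REML fits, four groups, correlation 0.85, 1000 trials per scenario, t test on N − 4 degrees of freedom:

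| SD growth | Homogeneous AR(1), complete data (N = 121) | Homogeneous AR(1), 20% dropout (N = 151) |
|---|---|---|
| none | 5.0% | 5.9% |
| 1.5-fold | 9.6% | 11.6% |
| 2-fold | 13.7% | 12.6% |
| 3-fold | 14.9% | not completed |

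In the 3-fold complete-data case, heterogeneous AR(1) gave 4.3% (SE ratio 1.02) and unstructured gave 4.3%. Monte Carlo error is about 0.7 to 1.1 percentage points. Data were normal with equal variances across arms and no covariates.

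**Is growth plausible?** Protocol 4.2 describes a pilot of oral ruxolitinib in which 9 of 12 patients regrew hair within 3 to 6 months, with a mean 92% reduction in hair loss. Suppose responders reach 92% and the rest 0%. The variance of relative change is 92²·0.45·0.55 = 2095 at a 45% response rate and 92²·0.10·0.90 = 762 at 10%. The average is 1428, an SD of about 38 at Week 24. Adding residual noise with an SD of 5 to 15 points gives about 38 to 41 at Week 24, against 5 to 20 at Week 4. The limiting rate was then 15–18% for linear regrowth and 9–15% if regrowth plateaus at Week 12 or 16.

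**The case against.** - **The SAP does not say one variance.** A reader might infer that it chose a homogeneous structure. It says only autoregressive, and heterogeneous AR(1) would satisfy the text with no inflation. This stands: the defect is an unspecified structure. Homogeneous AR(1) is the usual meaning of the unqualified word.
- **The size is assumed.** A reader might conclude that the false-positive rate triples. That needs about 3-fold SD growth. At 1.5- to 2-fold the limiting rate is about 2 to 2.6 times nominal, and with constant SD there is no inflation. This stands.
- **The fallback is unlikely to be reached.** SAP 8.3.1 fills missing SALT scores by LOCF or interpolation. If the MMRM uses those data, the visit grid is nearly complete, and 21 parameters on about 150 patients is a modest demand. In simulated data (SD 10 to 37, correlation 0.85), the residual covariance was positive definite in 2000 of 2000 runs with 151 patients, 20% dropout and LOCF, and likewise for completers only (about 121, and about 91). This tests singularity, not the software's iterations, but it stands as a judgement.
- **Per Protocol runs.** A reader might expect the smaller population to trigger the fallback more often. SAP 4.4 requires a Week 24 SALT score for that population, so its grid should be at least as complete. The documents do not support the inference.
- **Choice after seeing results.** A fit that fails to converge gives no usable p-value to select on. What remains is that step 2 has no order and no stopping rule.
- **All comparisons too optimistic.** They are not. Early visits become conservative.

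**Conclusion.** The point holds in a conditional form, and it is minor. SAP 8.4.2 permits one fallback that gives a Week 24 false-positive rate of about 10% to 17% and another that keeps it near 5%, and does not say which. The range assumes homogeneous AR(1), model-based standard errors and SD growth of 1.5- to 4-fold. The direction of growth is well supported for change from baseline; its size is not in the documents.

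Only the exploratory MMRM p-values for SALT score, absolute change and relative change are at risk, and only if the unstructured fit fails. The primary analysis and the stated sample size do not depend on it. It is still worth correcting, because a fallback should be valid in the case for which it is written.

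**What to change.** In SAP 8.4.2, replace the two fallback sentences with a fixed order: heterogeneous Toeplitz, then heterogeneous AR(1), then heterogeneous compound symmetry. Use the first that converges. Delete the step that leaves other structures to be explored, and keep descriptive statistics as the last step.

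Empirical (sandwich) standard errors can be added as a sensitivity check. They need not be mandatory: heterogeneous AR(1) with model-based standard errors already held 4.3% in the 3-fold case, and sandwich errors were not tested with about 29 to 43 patients per arm.

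The cost is SAP wording and code options, and slightly wider Week 24 intervals when the fallback is used. No data collection or patient numbers change.

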#### **Exploratory Efficacy Endpoints**

Treatment differences for relative change in SALT score from baseline to Weeks 4, 8, 12, 16, 20, and 24 will be assessed with a mixed-effect model of repeated measures (MMRM) model. The model will include fixed factors for treatment group, study visit, and treatment by study visit interaction, with baseline SALT score as a covariate. An unstructured variance-covariance matrix will be used.

Treatment differences for the Global Impression of Improvement and VAS scales will be assessed with the Cochran-Mantel-Haenszel test using the alopecia areata subtype as the stratification factor.

Change in symptoms as measured by AASIS and the exploratory questions from baseline to Week 24 will be assessed with the analysis of covariance with a fixed factor for treatment and baseline value as a covariate.

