1. PURPOSE OF THE STATISTICAL ANALYSIS PLAN

This statistical analysis plan (SAP) contains detailed information to aid in the implementation of the statistical analyses and reporting of the study data for use in the clinical study report (CSR) for study CP543.2001. This SAP is being written with due consideration of the recommendations outlined in the most recent International Conference on Harmonisation (ICH) E9 Guideline, entitled Guidance for Industry: Statistical Principles for Clinical Trials, and the most recent ICH E3 Guideline, entitled Guidance for Industry: Structure and Content of Clinical Study Reports.

This SAP describes the data sets that will be used for analysis, as well as patient characteristics, efficacy, safety, pharmacokinetic (PK), pharmacodynamic (PD), and clinician-reported and patient-reported perception of disease severity and improvement parameters. The details of the specific statistical methods stated in the protocol will be provided and any changes from the protocol-specified analyses will be documented in the SAP prior to database lock. Pharmacokinetic analyses are outside the scope of this document and will be performed and reported separately. If additional analyses are required to supplement the planned analyses described in this SAP after the database lock, they may be completed and will be described in the CSR. Table, figure, and listing specifications are provided as an attachment in a separate document. The CP543.2001 protocol amendment 2.0 was finalized on 05 July 2017. The purpose of this amendment was to revise for a new sequential cohort study design, where a parallel active dose comparison would no longer be conducted. Amendment 3.0, dated 25 September 2017, further clarifies this revised approach. Amendment 4.0, dated 17 August 2018, included an additional Cohort of subjects to assess a 12 mg BID dose of CTP-543 compared to placebo. The sample size calculations were updated to reflect the additional patients enrolled. Amendment 5.0, dated 21 January 2019, included language for allowing eligible patients who completed dosing for 24 weeks to enter an open-label extension study of CTP-543. This SAP is based on the latest protocol amendment.

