12. CHANGES TO THE ANALYSES PLANNED IN THE PROTOCOL

The following alterations were made to the original analyses planned in the protocol:

- SALT 50% reduction analysis changed from Cochran-Mantel-Haenszel Test (CMH) to χ^2 test and will not be stratified by Alopecia Areata subtype.
- VAS-S analysis method changed from CMH to ANCOVA.
- CGI-I and PGI-I analysis method changed from CMH test to χ^2 test.
- AASIS and Exploratory Question analysis method changed from ANCOVA to descriptive statistics and χ^2 test, respectively.
- Alopecia Areata subtype used as a fixed effect within the MMRM.
- TEAE definition modified so that all AEs that occur after study dosing will be counted, rather than only those that occur up to Week 24 or the Early Termination Visit.

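### The SAP names two different tests for the 7-point CGI-I and PGI-I, and leaves unclear whether the ordered one is run for each dose against pooled placebo

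*SAP*

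**What the plan says.** **Protocol 12.4.2, Exploratory Efficacy Endpoints.** The global impression scales were to be analysed by a stratified test: "Treatment differences for the Global Impression of Improvement and VAS scales will be assessed with the Cochran-Mantel-Haenszel test", with alopecia areata subtype as the stratification factor.

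**SAP 12, the list of changes.** This withdraws that plan: "CGI-I and PGI-I analysis method changed from CMH test to" a χ² test. Trend is not mentioned.

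**SAP 8.4.2.** For the full scales, a χ² "trend test will be used to analyze CGI-I and PGI-I between treatment groups overall". The next sentence adds χ² tests between treatment groups for the much improved and much worse groupings.

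**SAP 8.4 and Table 8-1.** The lead-in is "Table 8-1 gives an overview of the analysis methods that will be used for each of the efficacy variables". The CGI-I and PGI-I rows give Weeks 12 and 24 and a χ² test, again without trend. The footnote still defines CMH, although no row uses it. Section 8.4 also sets the general comparison rule: the placebo groups "will be pooled and compared to each active dose (4 mg, 8 mg, and 12 mg) individually", and the active doses are compared with each other.

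**SAP 1.** On departures from the protocol: "any changes from the protocol-specified analyses will be documented in the SAP prior to database lock".

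**The concern.** A programmer who follows section 8.4.2 and one who follows Table 8-1 would run different tests on the same data and could report different conclusions. If the trend test is intended, the list of changes in section 12 does not describe it. The trend test is itself incomplete: no category scores are given, and it is not stated whether the trend runs over dose, over response, or both.

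The scope is also unclear. *Overall* could mean one test across the four treatment groups, or the whole 7-point scale as opposed to the grouped responses. Elsewhere in 8.4.2 the same word is contrasted with *by visit*. Other analyses in that section state their comparisons: the SALT responder analyses follow the pairwise method of 8.4.1, and the MMRM and ANCOVA results are given by treatment comparison.

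CGI-I and PGI-I are two of the five exploratory objectives in SAP 2.1.2. If the test is left open until programming, the choice could be made after the data are seen.

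**Working it through.** **1. The plan's own figure.** The only power statement concerns the primary endpoint: 28 v 28 patients, 45% v 10%, two-sided 0.05, above 80%. With pooled proportion 0.275:

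z = [√28 × 0.35 − 1.96 × √(2 × 0.275 × 0.725)] / √(0.45 × 0.55 + 0.10 × 0.90) = (1.852 − 1.238) / 0.581 = 1.06, which gives power of 85.5%.

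The statement reproduces. There is no power statement for CGI-I or PGI-I.

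**2. The instructions side by side.**

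| Place | Test for the 7-point scale | Groups compared |
|---|---|---|
| Protocol 12.4.2 | CMH stratified by subtype (withdrawn by SAP 12) | Treatment differences |
| SAP 8.4.2 | χ² trend test | *Overall*, undefined |
| SAP Table 8-1 | χ² test | Not stated; 8.4 gives each dose v pooled placebo, and dose v dose |
| SAP 12 | χ² test | Not stated |

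Two live instructions remain.

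**3. Degrees of freedom.** Plain χ²: (2 − 1) × (7 − 1) = 6 pairwise and (4 − 1) × (7 − 1) = 18 for four groups. A linear trend test has 1. If the true difference lies along the ordering, all versions share roughly the same noncentrality. A noncentrality of 7.85 gives power of 0.80 at 1 df, 0.52 at 6 df and about 0.32 at 18 df.

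**4. Group sizes.** Cohort sizes are not stated. Assuming n per dose, the 2:1, 2:1 and 5:1 ratios give placebo n/2 + n/2 + n/5 = 1.2n, for a total of 4.2n. With 150 randomised, n = 150 / 4.2 = 35.7 and placebo = 42.9, so about 36 and 43. The SAP's own powering size is 28 per group.

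**5. Simulated power, assumed distribution A.** Placebo percentages over categories 1 to 7 are 5/8/17/40/12/10/8. Proportional-odds shifts towards improvement have log-odds ratios of 0.1, 0.6 and 1.2 for 4, 8 and 12 mg. At 12 mg the proportion much or very much improved rises from 13% to 33%: odds 0.13/0.87 × e^1.2 = 0.496, and 0.496/1.496 = 0.33. The ordered test is (N − 1)r² on 1 df with category scores 1 to 7. Figures carry a simulation error of a point or two.

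| Comparison | Plain χ² | Ordered, 1 df |
|---|---|---|
| 12 mg v placebo, 36 v 43 | 51% | 82% |
| 12 mg v placebo, 28 v 28 | 32% | 65% |
| Four groups, 43/36/36/36 | 41% | 86% |

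At the larger size the two tests disagree on significance in about 34% of trials pairwise and 48% across four groups.

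**6. A second assumed distribution, B.** With 28 per group, placebo 3/7/20/45/13/7/5% and 12 mg 25/20/20/25/5/3/2%, power for 12 mg v placebo is about 65% plain and 86–87% ordered. The two tests disagree in 26–27% of trials. Across four groups and three dose patterns, power is 47–82% plain and 85–98% ordered. With no treatment effect, plain χ² rejects in about 3–4% of trials and the ordered test in about 5%; they disagree in 7–8%.

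**7. Sparseness.** Under B, the expected count per group in category 1 is 28 × (0.03 + 0.25)/2 = 3.9. The seven values are 3.9, 3.8, 5.6, 9.8, 2.5, 1.4 and 1.0, so five of seven are below 5.

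**The case against.** A trend test is a kind of χ² test, and section 8.4 says only that Table 8-1 "gives an overview of the analysis methods that will be used for each of the efficacy variables". The entries in Table 8-1 and section 12 may therefore be shorthand for the test that 8.4.2 gives in more detail. The table shells, a separate attachment not seen here, may settle the programming. This is a fair reading and limits the severity. It does not remove the discrepancy: section 12 is the formal record of changes and omits the trend, and 8.4.2 still lacks scores, axis and scope.

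The power figures rest on assumed distributions, and a monotone dose shift favours a trend test. That stands. The ordered test led in every non-null scenario run, but the size of the gap varies widely.

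Dropping stratification is a declared choice that matches the primary responder analysis. That also stands: it is not an inconsistency, and no figure for its cost is available.

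Two stronger readings are tempting and are not supported:

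- **Three tests in conflict, counting the protocol's CMH.** Section 12 of the SAP withdraws the CMH openly, by the route that section 1 announces.
- **No dose tested against placebo on the 7-point scale.** Section 8.4 requires each dose to be compared individually with pooled placebo, and *overall* may simply mean the full scale.

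**Conclusion.** The SAP contradicts itself on the 7-point CGI-I and PGI-I. Section 8.4.2 names a trend test; Table 8-1 and section 12 name a χ² test without trend. It is also unclear whether the trend test is pairwise, across all four groups, or both.

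The choice can change the reported result. In the assumed scenarios the plain test loses roughly 20 to 33 percentage points of power for 12 mg against placebo. A reader might infer that the plain test has half the power in general. That describes the 18-df four-group version (41% v 86%) and the 28-per-group pairwise case (32% v 65%) under distribution A. It does not hold for the larger groups (51% v 82%) or under distribution B (about 65% v 86%).

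Severity is minor. The endpoints are exploratory, no multiplicity adjustment is planned, the tests of the grouped improved and worse responses are specified consistently, and the primary SALT analysis is untouched.

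**What to change.** Name one method in the same words in SAP 8.4.2, Table 8-1 and section 12:

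- **Test:** CMH row mean scores, category scores 1 to 7, stratified by the randomisation subtype. It has 1 df for two groups.
- **Comparisons:** each dose against pooled placebo, at Weeks 12 and 24.
- **Supportive:** a four-group trend test, with the dose and response scores stated.

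Replace *overall* with the comparisons intended, and make section 12 describe the final method.

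The stratification is a recommendation that goes beyond reconciling the text. It partly restores the protocol's plan, and it agrees with the SAP's use of subtype in the MMRM and ANCOVA. If the authors prefer to keep the unstratified analysis, an unstratified ordered test stated identically in the three places would still resolve the contradiction.

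The cost is SAP wording and one procedure option, before database lock. No new data are needed.
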